36.	Partial Waiver of Consent for Screening/Recruitment	25
37.	Partial Waiver of HIPAA Authorization for Screening/Recruitment.....	26
38.	Waiver of Documentation of Consent	26
39.	Alteration of Consent.....	27
40.	Full Waiver of Consent/Parental Permission.....	28
41.	Full Waiver of Consent/Parental Permission (Public Benefit or Service Programs)	
	29	
42.	Full Waiver of HIPAA Authorization (Checklist).....	29
43.	Other Waiver Types (Checklist).....	30

44.	Vulnerable Populations (Checklist).....	30
45.	Medical Devices (Checklist).....	36
46.	Export Control (Checklist)	37
47.	Data Transfer/Sharing (Checklist).....	37
48.	Specimen Transfer/Sharing (Checklist).....	38

1. Objectives

1.1. Describe the purpose, specific aims, or objectives.

Our long-term goal is to develop a mindfulness-based intervention (MBI) program that significantly decreases stress/burnout and increases belongingness and connectedness among nurse faculty and staff. The overall objective of this pilot project, which is the next step in toward achievement of our long-term goal, is to examine the feasibility and preliminary efficacy of MBIs as an intervention for University of New Mexico (UNM) Health Sciences Center (HSC) nurse faculty and staff. Our central hypothesis is that this MBI intervention will improve the psychosocial outcomes (sense of belonging) and physiological outcomes (HRV) among HSC nurse faculty and staff. To test our central hypothesis and attain the overall objective, we will pursue the following specific aims:

Aim 1. To evaluate the feasibility and acceptability of MBIs (meditation or yoga) for HSC nurse faculty and staff. Acceptability will be assessed qualitatively from analyses of interviews with participants. Feasibility will be assessed as rates of recruitment, retention, and adherence to the MBI (% training sessions attended).

Aim 2. To evaluate the preliminary effect of MBI (meditation; yoga) in HSC nurse faculty and staff on: psycho-social outcomes (burnout; sense of belonging, stress, anxiety) and physiological outcomes (HRV evaluated by wearable electronics). We hypothesize that: a) psycho-social outcomes will improve post-intervention and b) physiologic measures (HRV) will improve post intervention compared to preintervention.

1.2. State the hypotheses to be tested.

Our central hypothesis is that this MBI intervention will improve the psychosocial outcomes (sense of belonging) and physiological outcomes (HRV) among HSC nurse faculty and staff.

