5.3. Provide sample size justification

The planned overall sample size of 30 is consistent with recommendations for pilot studies seeking to build evidence in the context of medium effect size differences between two groups.¹⁸

6. Study Timelines

6.1. Describe:

- *The duration of an individual subject's participation in the research*
- *The duration anticipated to enroll all subjects*
- *The expected duration for the investigators to complete the study (complete analysis)*

Participants will be enrolled until the allotted 30 participants for the first 6 weeks of the study is reached. The study is comprised of a pre-intervention assessment, followed by 6 weeks of meditation/yoga attendance (twice/week). Upon completion of the 6-week intervention, participants will complete a post intervention assessment (See Table 1.).

Table 1. Study Timeline	Months									
	1	2	3	4	5	6	7	8	9	10
Prepare research and data management tools.		→								
Session 1										
Recruitment		→								
Intervention		→	→							
Data Collection		→	→							
Preliminary Data Analyses				→						
Session 2										
Intervention				→						
Data Collection				→						
Analyses					→					
Prepare R01 proposal										→
Dissemination										→

7. Study Endpoints: Primary endpoint(s) are typically efficacy measures that address the main research question. Secondary endpoints are generally not sufficient to influence decision-making alone, but may support the claim of efficacy by demonstrating additional effects or by supporting a causal mechanism.

7.1. *Describe the primary and secondary study endpoints.*

Primary outcomes of interest of this study include the feasibility and acceptability of mindfulness-based interventions (MBI) (Aim 1). We will also examine the preliminary effect of these interventions on psychosocial outcomes (primary: sense of belonging; secondary: burnout, stress) and physiologic outcomes (HRV) (Aim 2).

7.2. *Describe any primary or secondary safety endpoints.*

This is a minimal risk study.

7.3. *Describe any exploratory endpoints.*

N/A There are no anticipated exploratory endpoints.

8. Research Setting

8.1. *Describe the sites or locations where your research team will conduct the research.*

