Participants who express interest and meet inclusion criteria will meet with the PI or trained research personnel to review the study protocol, including risks and benefits. Participants will be asked to read and sign the informed consent (Attachment C) and HIPPA agreement following the procedure described in Section 25 – Consent Procedure.

Baseline Assessment session: During the baseline assessment session, participants will be administered a structured questionnaire with a research team member via the secure REDCap system. Baseline self-report questionnaires will be completed: 1) Sense of Belonging Scale (SBS); 2) Mindfulness Attention Awareness Scale (MASS) 15-item; 3) Generalized Anxiety Disorder-7 (GAD-7); 4) NIH toolbox measure of perceived stress

Sample Descriptors: Sociodemographic characteristics (age, sex, physical ability, staff vs faculty, years in profession, years employment at HSC, previous mindfulness practice) will be assessed at the baseline session.

Assessment of belonging: Belonging will be assessed using the 8-item Sense of Belonging Scale (SBS). The SBS measures the sense of belongingness or feelings of acceptance and inclusion in a community experienced by an individual.²¹ The SBS was developed to be adapted to specific contexts.²¹ Using the method described by Mellinger and Park (2023), we adapted the scale to be specific to UNM HSC nurse faculty and staff. Response categories range from 1 (*Strongly disagree*) to 5 (*strongly agree*). Responses are summed and the mean is calculated with higher scores corresponding to a stronger sense of belonging.²² The SBS-8 demonstrated high levels of reliability with a Cronbach's alpha coefficient of .96.²¹

Assessment of mindfulness: *Trait mindfulness:* Trait mindfulness will be assessed using the 15-item Mindfulness Attention Awareness Scale (MAAS).²³ The MAAS was designed to assess core characteristics of mindfulness. The MAAS has demonstrated consistent reliability with Cronbach's alpha coefficients ranging from .80 to .90 in undergraduate, community, and nationally sampled adult populations.²³

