Assessment of burnout: The Copenhagen Burnout Inventory is a valid and reliable, 19-item, self-report measure of burnout.²⁴ Originally designed to measure burnout in among human service workers, it includes 3 scales. The personal burnout scale has six items and measures prolonged physical and emotional exhaustion. The work-related burnout scale has seven items that measure prolonged physical and emotional exhaustion secondary to work. The third scale, client-related burnout, has six items that measure burnout related to working with clients (client may be patients, students, service recipients). Each subscale can be scored separately.²⁴ The three subscales have demonstrated good reliability and criterion related validity in a variety of samples.^{24,25}

Assessment of anxiety and stress: The Generalized Anxiety Disorder-7 screener (GAD-7) is a 7-item self-report-measure of generalized anxiety disorder.²⁶ Response categories range from 0 (*Not at all*) to 3 (*Nearly every day*). Responses are summed (range, 0 to 21) with higher scores corresponding to more severe levels of anxiety. Using a cut-off of 8, the GAD-7 has a sensitivity of 92% and specificity of 76% for diagnosis of generalized anxiety disorder.^{27,28} The NIH toolbox measure of perceived stress is a 10-item fixed form. Responses are measured on a 5-point Likert scale ranging from 1 (*Never*) to 5 (*Very Often*) with higher scores indicating higher levels of perceived stress.^{29,30}

Brief Reflective Feedback: At the end of each mindfulness session, participants will be given a card on which to write two words that embody how they are feeling right now (no

identifying information will be on the card). Participants will be asked to share their two words with the group if they feel comfortable.

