For each yoga class, the instructor will lead the student through a series of yoga poses. Class will begin with centering and breathwork (pranayama) for 5-10 minutes. This will be followed by a series of warm-up poses (~5-10 minutes). After the warm-up sequence, students will flow through traditional sun salutations (~10-15 minutes). This will be followed by a series of standing poses (~ 15 minutes). Students will then be guided to flow through a series of cool-down poses on the floor (~10 minutes). Class will conclude with traditional Savasana during which affirmations or meditation are provided (~5-10 minutes).

Treatment fidelity:

Delivery: Standard treatment manuals and checklists have been developed. To ensure that the interventions are delivered as intended, yoga instructors will complete standardized checklists after each in-person session.³⁹ In addition, we will select one yoga session every 2 weeks for rating by trained research personnel. The PI and interventionists will meet to discuss results and problem solve. We will track participant's completion of study components using summary sheets for each visit. Participants will log attendance at intervention sessions using the mEMA app.

Post-intervention session: During the post-intervention assessment session, participants will be administered a structured questionnaire with a research team member via the secure REDCap system. Self-report questionnaires will be completed: 1) Sense of Belonging Scale (SBS); 2) Mindfulness Attention Awareness Scale (MASS) 15-item; 3) Generalized Anxiety Disorder-7 (GAD-7); 4) NIH toolbox measure of perceived stress. Participants will complete semi-structured (See Attachment G) interviews to help us collect data pertaining to the MBIs and delivery preferences. Interview responses will be transcribed in the REDCap system. These data will be used to adjust the content and format of the intervention based on feedback from participants who are our intended users.

13. Data Analysis

13.1. Describe the data analysis plan, including any statistical procedures.

Consistent with the scope of pilot projects, the proposed study will allow us to examine barriers to successful completion of the study, evaluation of acceptability of methods to participants, and estimates for future power analysis for a subsequent NIH R01 application. Numerical and graphical summaries will be computed for all measurements.

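### Burnout is a named secondary outcome, but its questionnaire appears in none of the assessment lists, so the plan as scheduled collects no burnout data

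*Combined protocol and SAP*

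**What the plan says.** Aim 2 in section 1.1 lists the outcomes as "psycho-social outcomes (burnout; sense of belonging, stress, anxiety) and physiological outcomes (HRV evaluated by wearable electronics", and the long-term goal in the same section also refers to reducing burnout. Section 7.1 sets the tiers: "psychosocial outcomes (primary: sense of belonging; secondary: burnout, stress".

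Section 12.3 describes the instrument: "The Copenhagen Burnout Inventory is a valid and reliable, 19-item, self-report measure of burnout". It has three scales that may be scored separately. The paragraph does not say when the inventory is given.

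The questionnaires for each session are set out in numbered lists. The baseline list appears in section 12.3 and again in section 12.5. Both begin "Baseline self-report questionnaires will be completed: 1) Sense of Belonging Scale (SBS); 2) Mindfulness Attention Awareness Scale (MASS) 15-item" and end "3) Generalized Anxiety Disorder-7 (GAD-7); 4) NIH toolbox measure of perceived stress". The post-intervention list in section 12.5 begins "Self-report questionnaires will be completed: 1) Sense of Belonging Scale (SBS); 2) Mindfulness Attention Awareness Scale (MASS) 15-item" and ends "3) Generalized Anxiety Disorder-7 (GAD-7); 4) NIH toolbox measure of perceived stress. Participants will complete semi-structured".

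Section 13.1 compares change from baseline between the groups with non-parametric tests and reports Cohen's d within and between groups.

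**The concern.** An outcome, its instrument and its schedule should agree. Here the first two are present and the third is missing. Staff or a database builder working from any of the three lists would administer four questionnaires and leave burnout out.

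The analysis in section 13.1 needs a value at both sessions. Without a baseline there is no change score and no within-group effect size. The baseline has to be taken before the six weeks of sessions, so an omission noticed after a cohort starts cannot be repaired for that cohort. One stated purpose of the pilot is to supply estimates for the power analysis of a later grant application. For burnout it would supply none.

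**Working it through.** There is no sample-size or power figure to reproduce. The check sets the instruments described in section 12.3 against every place where a questionnaire is scheduled.

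| Session questionnaire | Items | Measures | Baseline list, 12.3 | Baseline list, 12.5 | Post-intervention list, 12.5 |
|---|---|---|---|---|---|
| Sense of Belonging Scale | 8 | belonging | yes | yes | yes |
| MAAS (trait) | 15 | mindfulness | yes | yes | yes |
| GAD-7 | 7 | anxiety | yes | yes | yes |
| NIH perceived stress | 10 | stress | yes | yes | yes |
| Copenhagen Burnout Inventory | 19 | burnout | no | no | no |

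Four of the five instruments are in 3 of 3 lists. The burnout inventory is in 0 of 3.

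Other places that could supply a time point:

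- **Mobile assessment (12.3).** The only survey scale named is the 5-item MAAS-State.
- **Schedule of activities (12.4).** The heading has no response under it.
- **Post-intervention interview (12.5).** It covers the interventions and delivery preferences and would not yield an inventory score.
- **Feedback cards (12.3).** Participants write two words and the cards carry no identifier.

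None of these schedules burnout.

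Size of the gap, per participant: 2 sessions need a burnout score and 0 are scheduled. Across the study, section 5.2 allows up to 60 participants, so 60 × 2 = 120 assessments at most, with 0 scheduled. For the first cohort of 30 alone, 30 × 2 = 60.

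Burden of the correction: the listed battery is 8 + 15 + 7 + 10 = 40 items. The inventory's scales sum to 6 + 7 + 6 = 19, which agrees with its stated length. Adding it gives 40 + 19 = 59 items per visit, an increase of 19/40 = 47.5%.

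A related mismatch runs the other way. Anxiety is an Aim 2 outcome and GAD-7 is in all three lists, yet section 7.1 names only burnout and stress as secondary. Those data would be collected but have no tier.

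**The case against.** The strongest reply is that the intention to measure burnout is plain. The inventory is described under data collection in the same format as the four listed instruments, and the lists do not claim to be exhaustive. The three lists share the same misspelled abbreviation for the MAAS, so they look like one text reused: a single drafting slip, not three independent statements. The attachments and the REDCap build are not available and may include the form.

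It can also be said that the stakes are limited. The main aims are feasibility and acceptability, the primary psychosocial outcome is belonging, and belonging is in every list. The count of 120 is a ceiling that assumes full enrolment and no dropout. The second cohort starts after the first finishes, so an error found in time would cost only the first cohort's baseline.

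Most of this is fair as a limit on the claim. Actual loss of data is a risk and not a certainty, and no primary outcome is affected. But evident intent does not supply a time point, and a slip copied into every list leaves no correct list to consult. The protocol contradicts itself whatever the database contains.

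**Conclusion.** The concern holds. A named secondary outcome, one of the two psychosocial ones in section 7.1, has an instrument but 0 of 2 required measurements scheduled for each participant.

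The conclusion concerns the plan as written. That burnout data would in fact be lost rests on the assumption that the forms and visit procedures follow the stated lists, which cannot be checked from the protocol. Because a missed baseline is irrecoverable and the correction is small, it must be fixed before the first baseline session. The anxiety mismatch is a lesser, separate point of alignment.

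**What to change.** Reconcile sections 1.1, 7.1, 12.3 and 12.5 in one of two ways.

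1. **If burnout is to be measured:** add the 19-item Copenhagen Burnout Inventory as the fifth questionnaire in both baseline lists (12.3 and 12.5) and in the post-intervention list (12.5). State which subscale or subscales carry the secondary outcome, since they can be scored separately and no section chooses. Confirm that the REDCap build has the form at both visits.
2. **If it is not to be measured:** remove burnout from Aim 2 and section 7.1, and delete the instrument description.

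In either case, add anxiety (GAD-7) to section 7.1 so that outcomes and questionnaires match, and complete section 12.4 with an instrument-by-visit schedule.

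The cost of the first option is a few lines of text, one form at two visits, and 19 more items per visit (40 to 59). Burden is one of the acceptability domains under Aim 1 in section 13.1, so the added length should be acknowledged there. The second option costs only wording, but gives up an outcome that the long-term goal names.

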- Mothers who are minors cannot enroll their child into a research study without the consent of their parent or parents, as applicable. Clarify if applicable.
- Minors in foster care must be excluded from research per NM state law. Please state minors in foster care will be excluded, if applicable.
- Minors that are wards of the state must have additional safeguards met; Please consult with the HRPO if not excluding minors who are wards of the state. Otherwise state that wards of the state will be excluded.
- Prisoners Yes No; If yes, please contact HRPO; Inclusion of prisoners requires approval from the Office for Human Research Protections (OHRP) and from the NM Corrections Department.
- Non-English speakers Yes No; If yes, please clarify specific languages enrolling: **Note:** State congruently in section 25. Consent Process, subsection, Subjects not fluent in English.

4.4. Indicate if you excluding any particular populations (e.g., women, children, persons not fluent in English, a particular racial or ethnic group, etc.) and provide justification.

This study excludes individuals under that age of 18 due to the focus on adult faculty and staff employed at the UNM HSC. We will exclude pregnant individuals due to specific activity modifications that would be required to assure the safety of these individuals during yoga. We will not recruit individuals unable to provide written consent in English.

4.4.1. If excluding pregnant women, please indicate how investigators will screen for pregnancy.

5. Number of Subjects

5.1. If this is a multicenter study, indicate the total number of subjects to be accrued across all sites.

N/A. this study is not a multicenter study.

5.2. Indicate the number of subjects to be recruited at this site.

We will enroll 60 faculty and staff in this study. Once we have enrolled 30 participants, we will waitlist individuals for a second six-week intervention session after the completion of the first session. This will result in a possible enrollment 60 individuals.

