Feasibility of recruitment: The UNM CON currently employs 71 faculty members and 71 staff members with additional nurse faculty in other HSC schools and colleges and the hospital. The planned overall sample size of 30 per cohort is consistent with recommendations for pilot studies seeking to build evidence in the context of medium effect size differences between two groups.¹⁸ Furthermore, objectives of pilot studies include assessment of recruitment and retention rates.¹⁸

The UNM College of Nursing is housed in the College of Nursing/College of Population Health Building. The UNM College of Nursing has a state-of-the-art Research Laboratory suite that includes private clinical research rooms as well as a large collaborative research space to conduct the intervention.

This is a minimal risk study that is not expected to have adverse psychological or medical consequences for participants. However, if needed there are providers available for referral and referral procedures are described below in Section 18 - Risks to Subjects.

Prior to beginning recruitment and enrollment, all study personnel will be trained on the protocol as well as consent and interview procedures for the study. All study personnel will have completed training for the ethical conduct of research. Study coordinators will routinely monitor the approved study team member list to ensure all team members remain current in their training.

10. Prior Approvals

- 10.1. *Describe any approvals that will be obtained prior to commencing the research. (e.g., school, external site, funding agency, laboratory, radiation safety, or biosafety approval.)* N/A
- 10.2. *Upload the required Departmental Review Form signed by your Department Chair (or authorized designee if the PI is the Department Chair) into Huron IRB under “supporting documents.” The signed, required Departmental Review form has been uploaded under “supporting documents”.*

10.3. If a study includes ionizing radiation, the Radiation Safety Attachment (HUS-FORM_1) must be uploaded (attached) in Huron IRB with your submission. The consent should include radiation exposure information in the Risks section.

N/A

10.4. If applicable to the study, include the signed “Biological Specimens” and/or “Drug Attachment” in Huron IRB with your submission.

N/A

11. Multi-Site Research

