The UNM CON currently employs 71 faculty and 71 staff and the HSC has additional nurse faculty and staff. We will employ a quasi-experimental design to assess feasibility, acceptability, and preliminary efficacy of MBIs (meditation; yoga) to increase a sense of belonging and connectedness in academic nursing faculty and staff. Using convenience sampling we will recruit and enroll 60 participants in to two study groups: 1) mindfulness mediation and 2) yoga. Interested study participants will be contacted by study staff and screened to determine study eligibility (See Attachment A). The screener is approximately 1-page in length and takes approximately 5 minutes to complete. The screener includes queries related to inclusion and exclusion criteria. Participants will also complete an Exercise Participation Screening (see Attachment B).¹⁷

Pre-data collection:

We will assign 15 individuals to each condition. Across both conditions, all participants will participate in one baseline assessment/training session, 6 weeks of MBIs (participants will be required to attend 2 sessions per week), and a post-intervention assessment session. Following screening for inclusion/exclusion criteria, eligible participants will complete the BEING Mindful Exercise participation screening. Eligible participants will provide informed consent.

After informed consent is obtained, research staff will allocate individuals to meditation vs yoga on 1:1 basis. If an individual is unable to participate in the yoga arm based on the BEING Mindful Exercise participation screening, they will be assigned to meditation and the next two participants will be assigned to yoga.

All participants will be given an anonymous study ID number once they are enrolled in the study. The only link between the study ID number and any identifier will be stored in a secure N:\Research-Studies network drive, in a folder to which only the investigators will have access. Any link between the study ID and identifiers will be destroyed when data analysis is complete.

Once we have enrolled 30 participants we will waitlist individuals for a second six-week intervention session after the completion of the first session. This will result in a possible enrollment 60 individuals.

12.3. For studies that collect existing or prospective data, describe the source of information, whether collected prospective or retrospectively.

Data collection:

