Description of Intervention Delivery

These guidelines detail the procedures used to conduct Mindful Meditation or Yoga sessions.

We will employ a quasi-experimental design to assess feasibility, acceptability, and preliminary efficacy of MBIs (meditation; yoga) to increase a sense of belonging and connectedness in academic nursing faculty and staff. We will assign 15 individuals to each condition. Across both conditions, all participants will participate in one baseline assessment/training session, 6 weeks of MBIs (participants will be required to attend 2 sessions per week), and a post-intervention assessment session. Following screening for inclusion/exclusion criteria, eligible participants will complete the **BEING Mindful** Exercise participation screening. Eligible participants will provide informed consent.

Assignment of Participants:

After informed consent is obtained, research staff will allocate individuals to meditation vs yoga on a 1:1 basis. If an individual is unable to participate in the yoga arm, they will be assigned to meditation and the next two participants will be assigned to yoga.

Retention:

To promote retention, we will reach out to participants with frequent reminders via text messages and emails.

Baseline Assessment session: During the baseline assessment session, participant characteristics will be collected. Baseline self-report questionnaires will be completed: 1) Sense of Belonging Scale (SBS); 2) Mindfulness Attention Awareness Scale (MASS) 15-item; 3) Generalized Anxiety Disorder-7 (GAD-7); 4) NIH toolbox measure of perceived stress.

Intervention Delivery:

The meditation and yoga interventions are 6-week protocols. We will offer meditation sessions 4 times per week and yoga sessions 4 times per week. We will require participants to attend two sessions per week. Attendance will be tracked via the Ilumivu platform. Participants will be requested to log attendance at each session via the app.

The meditation intervention will be led by [name] and [name]. Meditation is a practice of mental exercises designed to increase focus and cultivate a desire to relieve suffering in self and other.^{35,36} The practice dates back millennia to Buddhist and Hindu sages, but more recent work focuses on stress.³⁷ More recently, the term mindfulness has been used which means awareness, attention, and remembering.³⁷ Many religious traditions have a form of meditation based practice. This study will focus

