Aim 1: To assess precision of estimates, 95% confidence intervals will be calculated for rates of recruitment into study, retention to end of study, and participants completing all training sessions. Overall adherence will also be described by calculating the mean and standard deviation of the number of completed training sessions per participant. Qualitative Analyses: Qualitative descriptive analysis⁴⁰ will be used to create a comprehensive summary of the acceptability of the MBI to participants. Deductive analysis will be used to determine common themes related to acceptability in the domains of affective attitude, burden, ethicality, intervention coherence, opportunity costs, perceived effectiveness, and self-efficacy.⁴¹ Interview responses will be reviewed by two members of the research team to identify themes. Themes and preliminary interpretations will be regularly presented to the larger research team to resolve any discrepancies or disagreements and check for alternative interpretations.

Aim 2: Participant characteristics and baseline survey responses will be described using means and standard deviations (SD) for continuous variables and number (percentage) for categorical variables. Continuous intervention outcomes will be described using means and standard deviations and, due to sample size, difference scores from baseline for intervention outcomes will be compared between groups using non-parametric statistical tests. Cohen's d, as a descriptive statistic, will be used as an effect size measure to quantify the extent of within group and between group differences in means over time.⁴² Long-term HRV (time domain and frequency domain measures derived for each 5 minute epoch within a 24 hour period will be averaged) measures will be compared between meditation and yoga groups by t-test. EMA and HRV data will be merged into a single dataset, matching upon timestamp.

Five-minute heart rate epochs immediately following completion of each mEMA survey will be selected for analysis.^{20,34}

13.2. Provide a power analysis, if applicable.

14. Provisions to Monitor the Data to Ensure the Safety of Subjects

This section is required when research involves more than Minimal Risk to subjects. Describe:

N/A – The PI believes this study constitutes no more than minimal risk for potential participants. Therefore, a Data and Safety Monitoring Plan is not required.

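### The plan does not say whether interview feedback may change the intervention for Session 2, and the Aim 2 comparison takes no account of session

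*Combined protocol and SAP*

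**What the plan says.** **Two consecutive sessions.** Section 5.2 states: "Once we have enrolled 30 participants, we will waitlist individuals for a second six-week intervention session after the completion of the first session". Sections 5.2 and 12.2 then add: "This will result in a possible enrollment 60 individuals". For each session, sections 12.2 and 12.5 give the arm size: "We will assign 15 individuals to each condition".

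**Use of the interviews.** Every participant has a semi-structured interview at the post-intervention visit. Section 12.5 commits the team to acting on it: "These data will be used to adjust the content and format of the intervention based on feedback from participants who are our intended users". No date, session or later study is named. Section 13.1 adds: "Themes and preliminary interpretations will be regularly presented to the larger research team".

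**Session 1 analysis.** Table 1 in section 6.1 has a row "Preliminary Data Analyses" in the Session 1 block, separate from the analyses row for Session 2. Its content, audience and purpose are not described.

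**Manuals.** Section 12.5 says that Attachments E (meditation) and F (yoga) standardise delivery. Nothing says that they stay fixed between sessions or that versions are recorded.

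**Analysis.** For Aim 2, section 13.1 compares change scores between groups with non-parametric tests, compares long-term HRV with a t-test, and uses Cohen's d descriptively. Session appears in none of these, and pooling is not mentioned. The sample size is described in two ways. Section 5.3 says: "The planned overall sample size of 30 is consistent with recommendations for pilot studies seeking to build evidence in the context of medium effect size". Section 9 says: "The planned overall sample size of 30 per cohort is consistent with recommendations for pilot studies".

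**The concern.** A pilot may refine its intervention as it goes, or it may estimate the effect of a fixed one. The plan does not say which it is doing. Session 1 interviews will be complete while Session 2 is still to be delivered or under way, and the adjustment sentence is a firm commitment with nothing to confine it to later work.

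If content or format changes between sessions, the primary feasibility results (retention, sessions attended, acceptability) and the Aim 2 summaries each average over two interventions. Section 13.1 says that these estimates will supply the power calculation for an R01 application. A blended effect size would then be used to plan a trial of one particular version. Even if nothing changes, the sessions differ in calendar time and in who was waitlisted, so an analysis that ignores session leaves out a known feature of the design.

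**Working it through.** **1. Head count (reproduces the plan's figure).** 15 per arm × 2 arms = 30 per session, and 30 × 2 sessions = 60. This agrees with sections 5.2 and 12.2. If the sessions are pooled, each arm has 15 + 15 = 30.

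**2. What the text permits.** The relevant statements, side by side:

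| Question | Answer in the plan |
|---|---|
| Will interview feedback change the intervention? | Yes (12.5) |
| From when? | Not stated |
| Are Attachments E and F held fixed between sessions? | Not stated |
| Are the two sessions pooled? | Not stated; 30 is overall in 5.3 and per cohort in 9 |
| Is session in the Aim 2 analysis? | No (13.1) |
| What does the Session 1 preliminary analysis contain? | Not stated (Table 1) |

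An investigator could therefore change the manuals after Session 1, pool all 60 without a session term, and still be within the protocol.

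**3. What a pooled effect would then mean.** With equal session sizes and a common SD, the pooled standardised difference is (d1 + d2)/2. Assume d1 = 0.5 in Session 1:

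| d2 in Session 2 (assumed) | Pooled d |
|---|---|
| 0 | 0.25 |
| 0.25 | 0.375 |
| 0.75 | 0.625 |
| 1.0 | 0.75 |

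In no row does the pooled value equal either session's effect. If the change moves both arms equally, the between-arm d is unaffected, but within-arm change still mixes two versions.

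**4. Precision, pooled and by session.** Assume an observed d = 0.5 and no dropout. The noncentral-t 95% interval uses t = d√(n/2) with 2n − 2 degrees of freedom.

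- 30 per arm: t = 0.5 × √15 = 1.94 on 58 df. The interval is −0.02 to 1.01, half-width 0.51.
- 15 per arm: t = 0.5 × √7.5 = 1.37 on 28 df. The interval is −0.23 to 1.22, half-width 0.73.

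The normal approximation 1.96√(2/n) gives nearly the same: 0.506 and 0.716.

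**5. Could the data show afterwards that the versions were equivalent?** With SD 1 (assumed) and 15 in each of four cells, the session-by-arm contrast has SE √(4/15) = 0.516. Its 95% half-width is 1.96 × 0.516 = 1.01 SD. The difference detectable with 80% power is (1.96 + 0.84) × 0.516 = 1.45 SD. A finding of no interaction would therefore be uninformative.

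**6. Price of stratifying.** In a linear analysis of all 60, two arm means leave 60 − 2 = 58 residual df, and adding session leaves 57. Because the design fixes 15 per arm in each session, arm and session are balanced and little precision is lost.

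**The case against.** The strongest reply is that the plan is silent rather than wrong. The adjustment sentence describes a visit that participants in both sessions attend. Section 1.1 presents the pilot as a step toward a later programme, and section 13.1 names the R01 directly after the adjustment sentence. Adjusting the later programme is at least as natural a reading. This stands, and a reader should not infer that Session 2 will be changed.

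Other inferences are tempting and equally unsupported:

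- **That the preliminary analysis comes before Session 2.** In Table 1 as extracted from the PDF, that row and the Session 2 intervention both fall in month 4, and arrow positions may be displaced. Row order is not chronology.
- **That the study lead, who leads the yoga arm (9.1) and has data access (16.2), will see interim results by arm.** The preliminary analysis may contain only Aim 1 rates. The meeting of the PI and interventionists in 12.5 concerns fidelity ratings.
- **That precision falls from 30 to 15 per arm.** This presumes pooling, which is implied by enrolling 60 but never stated. On the per-cohort wording in section 9, 15 per arm may be the plan's own precision.
- **That the arm comparison is biased.** Both arms run in each session, so a version change is not confounded with arm.

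It is also fair that feasibility and acceptability are primary, Cohen's d is descriptive, no decision rule depends on a pooled estimate, and refining from feedback is legitimate in a pilot. Manuals in both arms, with checklists and ratings for yoga, support consistent delivery, although they do not stop a manual from being revised.

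What the reply does not answer is that the text allows either course, and the analysis section would handle both in the same way.

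**Conclusion.** The concern holds as a gap in the plan that should be closed. The protocol commits to adjusting the intervention without saying from when, and analyses two consecutive sessions without reference to session. If content changed between them, pooled adherence, acceptability, within-arm change and Cohen's d would describe a mixture of versions, with version confounded with session and not with arm.

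The half-widths of about 0.51 (30 per arm) and 0.73 (15 per arm) rest on an assumed d of 0.5, full enrolment, no dropout and, for the first, pooling. The mixing figures are illustrations, because the documents give no effect sizes. The consequence is harder interpretation and a weaker input to the R01, not a demonstrated bias. It is not fatal to an open feasibility pilot, but the session-by-arm half-width of about 1.01 SD (SD 1, 15 per cell) means that the data could not settle the question once Session 2 is over.

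**What to change.** 1. **Section 13.1.** Stratify the Aim 2 between-group comparisons by session, for example with a stratified rank-sum (van Elteren) test for change scores and a linear model with session as a factor in place of the t-test for long-term HRV. Report Aim 1 and Aim 2 summaries by session as well as pooled. Stratifying removes a shift in level between sessions, but the pooled effect is still an average over them, so step 2 is also needed.
2. **Section 12.5.** State that Attachments E and F stay unchanged until Session 2 ends and that interview feedback is applied to the follow-on trial. If refinement between sessions is intended, say so, log dated versions, and do not present the pooled estimate as that of one intervention.
3. **Section 6.1.** State that the Session 1 preliminary analysis is limited to Aim 1 counts pooled over arms.

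The cost is a few sentences of protocol wording and one extra factor in the analysis. The real downside is that improvements suggested by Session 1 participants wait until Session 2 is finished.
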